## **9.1 Analysis sets**

Assignment of patients into the different analysis sets will be performed prior to locking the database and beginning the data analysis.

Summary statistics will be provided for patient disposition (completers and premature study discontinuations) in this long-term follow-up study.

A table on number and percentage of patients with each protocol deviation in this long-term follow-up study will be provided.

In addition, the number of patients per analysis set will be tabulated.

### **Enrolled set**

The Enrolled set will consist of all patients who were assigned a subject ID in this long-term follow-up study.

### **Safety set**

The Safety set will consist of all patients that received at least one dose of study drug in this long-term follow-up study.

### **Fingolimod safety set**

The fingolimod safety set will include all patients who entered the long-term follow up study and received at least one dose of fingolimod in any study, i.e., in the original core/extension MS studies or this long-term follow up study.

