### **4.1 Inclusion criteria**

Patients eligible for inclusion in this study have to fulfill all of the following criteria:

1. Written informed consent must be obtained before any assessment is performed.
2. Patients who have completed designated ongoing or planned Novartis global clinical trials with fingolimod and are unable to obtain fingolimod outside a clinical trial.

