### **4.2 Exclusion criteria**

Patients fulfilling any of the following criteria are not eligible for inclusion in this study:

1. Premature permanent discontinuation from any fingolimod study due to:
  - a. An adverse event or serious adverse event or laboratory abnormality.
  - b. Conditions leading to permanent study drug discontinuation.
2. Pregnant or nursing (lactating) women where pregnancy is defined as the state of a female after conception and until the termination of gestation, confirmed by a positive

hCG laboratory test (> 5 mIU/ml). Patients who temporarily or permanently discontinued from any fingolimod study because of pregnancy or nursing (lactating) can be re-enrolled.

3. Women of child-bearing potential, defined as all women physiologically capable of becoming pregnant, UNLESS they are using highly effective contraception during the study and for 2 months after stopping treatment. ‘Highly effective contraception’ defined as contraception which results in less than 1% unwanted pregnancies when used properly according to the label.  
Women are considered post-menopausal and not of child-bearing potential if they have had 12 months of natural (spontaneous) amenorrhea with an appropriate clinical profile (e.g. age appropriate, history of vasomotor symptoms) or have had surgical bilateral oophorectomy (with or without hysterectomy) or tubal ligation at least six weeks prior to baseline. In the case of oophorectomy alone, only when the reproductive status of the woman has been confirmed by follow up hormone level assessment is she considered not of child bearing potential.
4. Chronic disease of the immune system other than MS which may require immunosuppressive treatment.
5. Severe active infection or active chronic infection.
6. Previous treatment with cladribine, cyclophosphamide or mitoxantrone.
7. Treatment with monoclonal antibodies (including Natalizumab) in the past 3 months.
8. Uncontrolled diabetes (HbA1c>9%).
9. Macular edema at Baseline.
10. Any medically unstable condition that may interfere with the patient’s ability to cooperate and comply with the study procedures, as assessed by the treating physician.
11. Any of the following cardiovascular conditions:
  - a. myocardial infarction within the past 6 months prior to enrollment or current unstable ischemic heart disease;

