2.5 Analysis sets

The following analysis sets will be defined.

- **Enrolled set:** The enrolled set will include all patients who entered the long-term follow-up study part I (excludes long-term follow-up study screen failures), but will exclude patients with protocol deviation severity code of 8 (8=exclude from all analyses) in the long-term follow-up study part I.
- **Safety set:** The safety set will include all patients who entered the long-term follow-up study part I and received at least one dose of fingolimod in any study, but will exclude patients with protocol deviation severity codes of 5 (5=exclude from all safety analyses) and 8 (8=exclude from all analyses) in the long-term follow-up study part I. Note that all data reported in the long-term follow-up study part I will be analyzed, including assessments or events which started before the long-term follow-up study part I.
- **Fingolimod safety set:** The fingolimod safety set will include all patients who entered the long-term follow-up study part I and received at least one dose of fingolimod in any study, but will exclude patients with protocol deviation severity codes of 5 (5=exclude from all safety analyses) and 8 (8=exclude from all analyses) during the core study prior to entry to the long-term follow-up study part I. For patients with such protocol deviations after the core study, record level data associated with the protocol deviations will be excluded from the analysis.

- **Fingolimod full analysis set:** The fingolimod full analysis set will include all patients who entered the long-term follow-up study part I and received at least one dose of fingolimod in any study but will exclude patients with protocol deviation severity codes of 0 (0=exclude from all efficacy analyses) and 8 (8=exclude from all analyses) during the core study prior to entry to the long-term follow-up study part I. For patients with such protocol deviations after the core study, record level data associated with the protocol deviations will be excluded from the analysis.
- **Follow-up set:** The follow-up set will consist of all patients in the safety set who have any follow-up visit data or at least one safety record after the study drug discontinuation. It will be used for summary of adverse events and concomitant medications with occurrences after last dose of fingolimod only.

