9.1.2.2 Adverse events during the fingolimod treatment period

Unless otherwise specified, all non-serious adverse events with onset on or after first dose date of fingolimod among all studies to last dose date of fingolimod + 45 days are included. All serious adverse events (SAEs) with onset on or after the first dose date of fingolimod among all studies are also included in the summaries. Also, unless otherwise specified, adverse events will be summarized for the fingolimod safety set, by primary system organ class and preferred term, and will show the number of patients with at least one adverse event and the incidence rate of adverse events per 100 patient-years in each SOC or PT category.

The AE incidence rate (IR) is calculated per 100 patient-years. IR is defined as: the number of patients experiencing at least one event in a particular category, over the total patient-years of the “at risk” population for that event multiplied by 100. An underlying Poisson process for incidence rate within treatment group is assumed.

To calculate the total patient-years (time at risk) of the “at risk” population:

1. For patients who have a particular AE category, sum the number of days from first dose date of fingolimod among all studies to the first occurrence of that particular AE category

2. For patients who did not have a particular AE category, sum the number of days from first dose date of fingolimod among all studies to last dose date of fingolimod + 45 days.
3. Add the time at risk for patients who had a particular AE category with the time at risk for patients who did NOT have a particular AE category. This is the total time at risk of that AE category.
4. Divide the total time at risk by 365.25.

Incidence rate of adverse events will be presented for the fingolimod safety set and for the subgroup of fingolimod safety set patients from phase II/III studies, by SOC and PT. Incidence rate of AEs, excluding AE listed in the core data sheet, will be presented by PT. Incidence rate of AEs that fulfill the risk search term (defined in the case retrieval sheet) will be presented by risk name and lower level terms. Similarly, all above indicated AE IR summaries will be conducted for SAEs.

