To further evaluate the long-term AE rate (based on patient count and percentage) within a particular fingolimod treatment duration, an analysis based on yearly intervals since first dose of fingolimod will be conducted. For summaries on this set of patients, all AEs and SAEs with onset on or after first dose date of fingolimod (among all studies) to last dose date of fingolimod are included. Each yearly interval will contain 360 days. For example: Year 1 will consist of Day 1 to Day 360, Year 2 will consist of Day 361 to Day 720, Year 3 will consist of Day 721 to Day 1080, Year 4 will consist of Day 1081 to Day 1440, Year 5 will consist of Day 1441 to Day 1800, and so on. Patients will be summarized within a particular yearly interval if they have been receiving study treatment for at least one day in that particular interval. The number and percentage of these patients who have adverse events with onset date occurring during the interval will be summarized. For example, for the Year 1 group, patients with at least one day exposure to fingolimod will be included, and AEs with onset date occurring between Day 1 and Day 360 will be summarized. For the Year 2 group, patients with at least 361 days exposure to fingolimod will be included, and AEs with onset date occurring between Day 361 and Day 720 will be summarized. The same will be done for other intervals.

Adverse events summarized by year will include the following:

- Adverse events, by yearly interval, primary system organ class, and preferred term
- Serious adverse events, by yearly interval, primary system organ class, and preferred term
- Adverse events that fulfill the risk search term, by yearly interval
- Serious adverse events that fulfill the risk search term, by yearly interval

Intervals will be included based on the length of fingolimod exposure. Risk search terms are defined in Novartis' case retrieval sheet. Associated summaries will be presented by risk name and lower level terms.

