2.5 Analysis sets

The following analysis sets will be defined. Analyses done on the fingolimod safety set and fingolimod full analysis set summarize all data starting from first dose of fingolimod among all studies, while other analysis sets generally summarize all data from the study part 2 only.

- **Enrolled set:** The enrolled set will include all patients who entered the study part 2 (excludes long-term extension study screen failures), but will exclude patients with protocol deviation severity code of 8 (8=exclude from all analyses) in the study part 2.
- **Safety set:** The safety set is a subset of the fingolimod safety set and will include all patients who entered the study part 2 and received at least one dose of fingolimod in any study, but will exclude patients with protocol deviation severity codes of 5 (5=exclude from all safety analyses) and 8 (8=exclude from all analyses) in the study part 2. Note that all data reported in the study part 2 will be analyzed, including assessments or events which started before the study part 2, unless otherwise specified. For example, adverse events which may have been continuing at the end of the long-term follow-up

study part 1 may be recorded in the study part 2 database with updated end date. These adverse events will be reported in listings and summarized if event occurs after first dose of fingolimod among all studies.

- **Fingolimod safety set:** The fingolimod safety set will include all patients who entered the study part 2 and received at least one dose of fingolimod in any study, but will exclude patients with protocol deviation severity codes of 5 (5=exclude from all safety analyses) and 8 (8=exclude from all analyses) during the core study prior to entry to the long-term follow-up study part 1. For patients with such protocol deviations after the core study, record level data associated with the protocol deviations will be excluded from the analysis.

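### From-first-dose AE, SAE and risk-term rates (SAP Part I) and yearly AE tables (both SAPs) count pre-entry time in which a fatal or treatment-ending event would have kept the patient out of the analysis set

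*Protocol*

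**What the plan says.** **Set membership.** Protocol 9.1 defines the fingolimod safety set as "all patients who entered the long-term follow up study and received at least one dose of fingolimod in any study". SAP Part I, Section 2.5, has the same condition: "The fingolimod safety set will include all patients who entered the long-term follow-up study part I". SAP Part 2, Section 2.5, moves it to the later milestone: "The fingolimod safety set will include all patients who entered the study part 2".

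**Entry.** Protocol 4.1 admits "Patients who have completed designated ongoing or planned Novartis global clinical trials with fingolimod". Protocol 4.2, criterion 1, excludes "Premature permanent discontinuation from any fingolimod study due to" an adverse event, serious adverse event or laboratory abnormality, or a condition leading to permanent discontinuation of study drug. Women who stopped because of pregnancy may re-enrol.

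**Clock.** For patients without the event, SAP Part I, Section 9.1.2.2, will "sum the number of days from first dose date of fingolimod among all studies to last dose date of fingolimod + 45 days". For patients with the event, time runs from the same first dose to first occurrence. The method applies to AEs, SAEs and risk-search-term events. The yearly tables in Section 9.1.2.2 of both SAPs also start at first fingolimod dose, and count a patient in a 360-day column "if they have been receiving study treatment for at least one day in that particular interval".

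**What else is planned.** For D2399 alone, SAP Part I, Section 9.1.2.1, gives counts and percentages but no rate per patient-year. SAP Part 2, Section 9.1.2.1.2, does give a rate, with its clock starting at the first Part 2 dose. Neither SAP mentions delayed entry or states the limitation.

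**The concern.** Membership is settled by a later event, and that event screens on the outcome. A patient who died of a serious infection, or stopped permanently because of a malignancy, during a core or extension trial never reaches D2399. Such patients are missing from the numerator, while those who did enter contribute all their pre-entry years to the denominator.

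Protocol 1.1 says further long-term data are needed on rare or time-dependent events, the synopsis plans to compare rates across exposure durations, and the SAP Part I overview names opportunistic infections and basal cell carcinoma as topics. In Part I the from-first-dose SAE and risk-term rates and the yearly tables serve these aims. If a category often ends treatment, its rate is understated and every yearly column containing pre-entry time is depleted.

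**Working it through.** The documents state no rate or event count, so there is no planned figure to reproduce.

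**1. Closed form.** Let the event have constant rate λ, of which a constant share q is fatal or ends treatment. Given entry, the visible rate is (1 − q)λ before entry and λ after it. With s the pre-entry share of risk time:

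reported/true = [(1 − q)·pre + post]/(pre + post) = 1 − q·s.

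**2. Inputs, for scale only.**
- q: not given. Protocol 5.5.9 lets an SAE such as malignancy support stopping in individual cases, so q is neither 0 nor 1 for such events. I use 0.1, 0.25 and 0.5. The 10.5% and 14.1% AE discontinuation in Protocol 1.1 are shares of patients, not q.
- Pre-entry time P, phase II/III: uniform 2-7 years (Amendment 3 rationale, mean 4.5). Sensitivity: 2.5-8 (Amendment 4 rationale, mean 5.25).
- P, phase IIIb: 0.5 years, assumed.
- Time in D2399, F: 5 years (the 60 months in the SAP Part I overview). Sensitivity: 2 years for phase IIIb, whose original reimbursement endpoint was kept (Amendment 4 rationale).
- Phase II/III share: 30% to 70%, assumed.

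**3. Overall Part I rate.** s = mean(P)/mean(P + F).
- Lowest case, 30% phase II/III: mean P = 0.3×4.5 + 0.7×0.5 = 1.7; s = 1.7/6.7 = 0.254.
- Same inputs at 70%: mean P = 0.7×4.5 + 0.3×0.5 = 3.3; s = 3.3/8.3 = 0.398.
- Highest case, 70% with both sensitivities: mean P = 0.7×5.25 + 0.3×0.5 = 3.825; mean F = 0.7×5 + 0.3×2 = 4.1; s = 3.825/7.925 = 0.483.

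| q | s = 0.254 | s = 0.398 | s = 0.483 |
|---|---|---|---|
| 0.1 | 0.975 | 0.960 | 0.952 |
| 0.25 | 0.937 | 0.901 | 0.879 |
| 0.5 | 0.873 | 0.801 | 0.759 |

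A simulation of 2,000,000 patients under the SAP risk-time rule used a different mix (15% with no pre-entry time, 35% with 0.3-1 year, 50% with 1-7 years). Against a true 2.00 per 100 patient-years it returned 1.93 at q = 0.1 and 1.63 at q = 0.5. Counting only from D2399 entry returned 2.00 both times.

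**4. Early-loaded events.** If the hazard is not flat, s becomes the pre-entry share of expected events. Protocol Appendix 7 puts about 75% of macular edema cases in the first 3-4 months. With 75% of events in the first 4 months, the simulation mix gives a share of 0.77, against a time share of 0.36. For illustration, at q = 0.5 the ratio is 1 − 0.5×0.77 = 0.62 instead of 1 − 0.5×0.36 = 0.82.

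**5. Yearly columns.** Take λ = 1 per 100 patient-years and 50% phase II/III. A full 360-day column has true value 1 − exp(−0.01×360/365.25) = 0.98%. A patient's column value is 1 − exp{−λ[(1 − q)·pre + post]}, for the time on drug in that column.
- *Part 2.* A column wholly before Part 2 entry reads about 0.98×(1 − q): 0.88, 0.74 and 0.49 at q = 0.1, 0.25 and 0.5. These columns are uniformly low; any rise comes later.
- *Part I, phase IIIb F = 5.* Year 5 at q = 0.25: phase IIIb patients are all post-entry (0.98). For phase II/II​I patients about 0.51 of the column is pre-entry, giving 0.98×(1 − 0.25×0.51) = 0.86. The column is (0.98 + 0.86)/2 = 0.92, against 0.80 in Year 1.
- *Part I, phase IIIb F = 2.* Years 1-5 read 0.80, 0.86, 0.64, 0.81, 0.86 at q = 0.25, and 0.61, 0.74, 0.53, 0.63, 0.73 at q = 0.5. The Year 3 dip arises because phase IIIb patients leave at 2.5 years, about 0.53 years into a column that still counts them in full.

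**The case against.** The study is descriptive, with no inferential analyses planned, and the set definition is open about its condition. Part I also reports D2399-only exposure (Section 6.1) and D2399 AE counts, so a reader could form a rough within-study rate. That softens the problem without removing it. A descriptive rate can still be biased, and the D2399 counts can include onsets before entry.

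The size is also unknown: nothing in the documents supports a particular q for any named event, and at q = 0.1 the shortfall is only 2% to 5%. This stands, and is why the result is a range.

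A reader might go further and infer that a flat hazard will appear to rise over the early yearly columns. The documents do not support that as an expected pattern. In Part 2 the columns wholly before entry are level, in Part I the smooth rise vanishes when phase IIIb follow-up is 2 years, and an early-loaded hazard has a different shape again. The denominator rule in the later columns is a separate matter that also distorts the shape.

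Finally, delayed-entry yearly rates would be thinnest where depletion is greatest. With 2-7 years of prior exposure, phase II/III patients contribute nothing to Years 1-2. This stands and limits the remedy.

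**Conclusion.** The point holds for the Part I from-first-dose rates and for the yearly tables in both SAPs. The downward direction of the overall rate follows from the entry rules for any event with q above 0 and some pre-entry time.

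The table in the working gives its size if the hazard is flat, q is constant and the assumed exposure and study mix are right; for early-loaded events the shortfall is larger at the same q. It is small where events seldom end treatment and zero for patients first dosed in D2399.

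It would be wrong to infer that all pre-entry events are lost: those that did not end treatment are counted. Nor are all tables affected. Deaths and AEs leading to discontinuation tabulated within D2399, and the Part 2 incidence rate, are sound on this point. For the yearly tables the supportable conclusion is that columns with pre-entry time are depleted for treatment-ending events, so their shape is no evidence of a trend in either direction.

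**What to change.** 1. Keep the from-first-dose tables, title them *conditional on entry to D2399* (in Part 2, *conditional on entry to Part 2*), and state the limitation in both SAPs.
2. Add to SAP Part I, Section 9.1.2.2, incidence rates for SAEs and risk-search-term events, with risk time and events counted only from the first D2399 dose. A patient whose first event in the category preceded entry is not at risk. This brings in the from-entry clock that SAP Part 2, Section 9.1.2.1.2, already uses.
3. Base no statement about trend with exposure, for serious or treatment-ending events, on the yearly tables. Optionally, in Part I only, show delayed-entry yearly rates per patient-year on the time-since-first-fingolimod scale, for years that meet a minimum number of patient-years fixed in the SAP.

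The cost is SAP wording and a few more table runs on data already held. The optional yearly rates would be sparse in the early years, and exposure year would be partly confounded with source study, because early years would come mainly from patients with short prior exposure.

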### **Fingolimod Full Analysis Set**

The fingolimod full analysis set (FAS) will include all patients who entered the long-term follow-up study and received at least one dose of fingolimod in any study, i.e., in the original core/extension MS studies or this long-term follow up-study.

### **9.1.1 Subgroup**

All analyses including data collected during Study Part two will be conducted based on the subgroup of patients who entered Study Part Two, which includes all patients with at least one dose of study medication after completing Study Part One.

## **9.2 Patient demographics and other baseline characteristics**

Demographic and background information collected from the clinical studies (core & extensions) from which the patients are transferred to this long-term extension study will be summarized. Background information includes prior MS treatment including previous exposure to fingolimod, relevant medical history / current medical conditions, duration of the disease, and baseline EDSS. Identification of clinical study participation prior to transfer into this long-term extension study will also be provided. Summaries will be provided based on the enrolled set.

### **9.3 Treatments (study drug, rescue medication, other concomitant therapies, compliance)**

Use of concomitant medications in this long-term follow-up study will be listed and summarized based on the Safety set to support the analysis including data from Study Part One or based on the subgroup of patients who entered Study Part Two of the Safety set to support the analyses including data from Study Part Two.

## **9.4 Analysis of the primary variable(s)**

### **9.4.1 Variable**

Long-term safety will be assessed based on adverse events (AEs), laboratory and vital signs as well as other investigations performed when clinically indicated.

Analysis of the safety variables will be conducted on

[figure not shown]
- Safety set: for any analyses including data collected during the long-term follow up study only
- Fingolimod safety set: for analyses including data from first dose of fingolimod in the original core/extension study, if there is any, and in the long-term follow up study.

Given the nature of the design, the data will be presented using descriptive statistics and no inferential analyses are planned.

